1.3 Study objectives

[figure not shown]
The objectives of this study are: 1) to assess whether or not a meal containing low carbohydrate in the form of glucose and galactose is associated with less diarrhea compared to a high carbohydrate meal; 2) to assess the potential effects of supplements such as psyllium or calcium carbonate on alleviating diarrhea.

[figure not shown]
1.3.1 Primary objective(s)

Primary objective(s)	Endpoints related to primary objective(s)

• To assess the effects of meals with different carbohydrate content on diarrhea	
• Diarrhea (consistency and incidence)

• To assess the effects of supplements (psyllium and calcium carbonate) on diarrhea	
• Diarrhea (consistency and incidence)

1.3.2 Secondary objective(s)

Secondary objective(s)	Endpoints related to secondary objective(s)

• To assess the effects of LIK066 and carbohydrate in meal on fecal parameters	
• Stool samples (timing, assessment of consistency with Bristol stool chart, stool weight, and stool pH)

1.4 Study design and treatment

This study employs a randomized, open-label, two-part, three-period, cross-over design.

This is a non-confirmatory study. Each part of the study will enroll approximately 24 overweight or obese subjects, thus, a total of approximately 48 subjects will be enrolled for the entire study. In each part of the study, each subject will be randomized to one of the 3 treatment sequences shown in Figure 1-1 (Part A) and Figure 1-2 (Part B). Blocked randomization within each study part will be used.

Part A of the study will assess the effects of % carbohydrate (50%, 25% and 0%) in the breakfast meals on diarrhea when LIK066 is administered immediately before the breakfast.

Part B of the study will assess the effects of a concomitant treatment with a supplement (calcium carbonate or psyllium) on diarrhea when LIK066 is administered immediately before a breakfast meal with 50% carbohydrate.

The study will consist of an up to 24 day screening period, a 3 day baseline/run in period, and three periods of treatment of 3 days each with a 5 day washout period in between each treatment period. Study completion will occur 3 days after the last dose of LIK066.

The baseline, treatment and washout periods will be conducted with subjects being domiciled for approximately 25 days (see Figure 1-1 and Figure 1-2).

Figure 1-1 Part A: Effects of Carbohydrate in the Breakfast Meals*

Screening Period	Baseline Day -3 to -1	Sequence	Treatment Period 1 Day 1-3	Washout 5 Days	Treatment Period II Day 9-11	Washout 5 Days	Treatment Period III Day 17-19	Washout EOS Day 20-22
Day-28 to -4								
	Run-In	1 (n=8)	50% CHO		25% CHO		0% CHO	
	Run-In	2 (n=8)	25% CHO		0% CHO		50% CHO	
	Run-In	3 (n=8)	0% CHO		50% CHO		25% CHO	

* CHO = % carbohydrate content in the standardized breakfast meal

LIK066 50mg QD will be given in the morning immediately before the breakfast meal

Figure 1-2 Part B: Effects of Supplements in the Breakfast Meals**

Screening Period Day-28 to -4	Baseline Day -3 to -1	Sequence	Treatment Period 1 Day 1-3	Washout 5 Days	Treatment Period II Day 9-11	Washout 5 Days	Treatment Period III Day 17-19	Washout EOS Day 20-22
	Run-In I (n=8)	NS		Psyllium	CC			
	Run-In II (n=8)	Psyllium		CC	NS			
	Run-In III (n=8)	CC		NS	Psyllium			

** CHO = % carbohydrate content in the standardized breakfast meal (50%) for all groups

LIK066 (50 mg QD) and supplement will be administered immediately before the breakfast meal

NS = No supplement

CC = Calcium Carbonate (1 gram)

Psyllium = 6 grams

There will be no interim analyses planned for the study.

2 First interpretable results (FIR)

First interpretable results (FIR) will be provided for this trial.

The study FIR template (mock slides) can be found in CREDI in the study RAP folder Cabinets/CREDI Projects/L/LIK066/CREDI Studies/LIK066B2203/Administrative Files (study level)/RAP or RAMP Meeting/.

The template shows the analysis / results to be presented in the FIR. Study outputs required to be created at the time of the FIR will be highlighted in TFL shells document and marked as “Key” in the Programming Deliverables Tracker (PDT) output list.

3 Interim analyses

Not applicable.

4 Statistical methods: Analysis sets

For all analysis sets, subjects will be analyzed according to the study treatments received.

The safety analysis set will include all subjects that received any study drug. All subjects in the safety analysis set will be included in the safety data analysis.

The PD analysis set will include all subjects in safety analysis set with available PD (diarrhea) data post baseline and no protocol deviations with relevant impact on PD data. All subjects in the PD analysis set will be included in the PD data analysis.

For subjects for which the actual sequence of treatments received does not match the randomized sequence of treatments, the actual sequence will be used for analysis involving a sequence component if the actual sequence is one of the sequences planned in the study design. If the actual sequence is not one of the sequences planned in the study design, the randomized sequence will be used for analysis involving a sequence component but data points from periods in which the subject has not received the randomized treatment will be excluded from the analysis.

[figure not shown]
The analysis sets and protocol deviation codes are related as follows:

[figure not shown]
Table 4-1 Protocol deviation codes and analysis sets

Category Deviation code	Text description of deviation	Data exclusion
Subjects are excluded from PD and PK analysis in case of these protocol deviations:		Exclude subject from PD and PK analysis set
	All inclusion and exclusion criteria deviations	
TRT01	Subject received treatment sequence that do not belong to ones specified for the study	Only data points from periods different from randomized sequence will be excluded
TRT02	Subject doesn't have sufficient wash out per protocol	
COMD01	Subject received prohibited concomitant medication	

Summary of frequency of subjects in each analysis set will be provided and subjects excluded from each analysis set will be listed with reasons being excluded. All protocol deviation will be listed together with corresponding analysis set(s) being excluded when applicable.

If updates to this table are needed, an amendment to the SAP needs to be implemented prior to DBL.

6 Statistical methods for Pharmacodynamic (PD) parameters

All subjects within the PD analysis set will be included in the PD data analysis.

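### SAP Table 4-1, as it reads, drops the whole subject from the primary analysis for a short washout or prohibited medication; a period-level rule would keep clean earlier periods at little cost (minor)

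*SAP*

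**What the plan says.** Table 4-1 in SAP section 4 links deviation codes to analysis sets. Its lead-in is "Subjects are excluded from PD and PK analysis in case of these protocol deviations" and the action beside it is "Exclude subject from PD and PK analysis set". Four kinds of deviation follow:

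- inclusion or exclusion criteria deviations: no action of their own;
- TRT01, a sequence outside the design: "Only data points from periods different from randomized sequence will be excluded";
- TRT02, lack of "sufficient wash out per protocol": action cell blank as extracted;
- COMD01, "Subject received prohibited concomitant medication": action cell blank as extracted.

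The text above the table also treats TRT01 by period: "data points from periods in which the subject has not received the randomized treatment will be excluded from the analysis". SAP section 6, which contains the primary endpoint, states "All subjects within the PD analysis set will be included in the PD data analysis". SAP 6.1.3.1 and protocol 11.4.3 then use all available data without imputation, and the SAP assumes missing at random. The table may still be changed: "If updates to this table are needed, an amendment to the SAP needs to be implemented prior to DBL".

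**The concern.** Protocol 3.2 justifies the crossover by the lower variability of within-subject comparisons. A short washout can first affect Period 2, so Period 1 is always clean under TRT02. If only the second washout was short, the whole Period 1 to Period 2 contrast is clean. Medication first taken in Period 3 cannot change stools counted in Periods 1 and 2. The subject-level default discards these data.

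The result is uneven. A subject who drops out after Period 2 contributes two periods. A subject given a wrong treatment keeps the correctly treated periods. A subject with a Period 3 medication deviation contributes nothing, although Periods 1 and 2 are just as sound. At stake is precision in a small trial. Bias is not at issue.

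**Working it through.** **1. How the table reads.** The subject-level action stands at the head, and TRT01 is the only row that departs from it. The TRT02 and COMD01 cells are blank in the same way as the inclusion/exclusion row, where subject-level exclusion is clearly meant. The TRT01 wording cannot have been intended to span the other rows, because it refers to periods that differ from the randomized sequence. Subject-level exclusion is therefore the natural reading, subject to the state of the extracted table.

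**2. The plan's own numbers (protocol 11.7 and section 4).** 5 / (1 − 0.375) = 8 per sequence, so 8 × 3 = 24 per part and 48 in total, as stated. Powered completers: 5 × 3 = 15 per part. Expected completers: 36 / 2 = 18 per part.

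**3. Data discarded per affected subject.** Whole-subject rule: 3 periods × 3 days = 9 treatment days. Period rule after a Period 3 deviation: 3 days.

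**4. CI width.** Design: three cyclic sequences in equal numbers (protocol Table 6-1), fixed period and treatment effects, random subject effect, one summary value per period. Within-subject correlation ρ is assumed to be 0.3, 0.5 or 0.7. The information matrix is the sum over subjects of X′V⁻¹X, using only the retained periods. Widening = √(contrast variance with loss / contrast variance of full design) − 1, averaged over the three treatment contrasts and, for one affected subject, over the three sequences.

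One affected subject per part (ranges run over ρ = 0.3 to 0.7):

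| Retained for that subject | n = 24 | n = 18 |
|---|---|---|
| Nothing (whole-subject rule) | 2.25% | 3.08% |
| Two periods (one later period lost) | 0.92-1.06% | 1.26-1.45% |
| Period 1 only | 1.71-2.02% | 2.34-2.76% |

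Hand check: √(24/23) − 1 = 2.2% and √(18/17) − 1 = 2.9%. The exact values are slightly higher because removing one subject unbalances the sequences.

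**5. Average saving for COMD01.** Assume intake is equally likely in each period and treatment then stops. Intake in Period 1 saves nothing, intake in Period 2 leaves Period 1 only, and intake in Period 3 leaves two periods.

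- n = 18, ρ = 0.3: (3.08 + 2.34 + 1.26)/3 = 2.23%, a saving of 0.85 percentage points.
- n = 18, ρ = 0.7: (3.08 + 2.76 + 1.45)/3 = 2.43%, a saving of 0.65 points.
- n = 24, ρ = 0.3: (2.25 + 1.71 + 0.92)/3 = 1.63%, a saving of 0.62 points.
- n = 24, ρ = 0.7: (2.25 + 2.02 + 1.06)/3 = 1.78%, a saving of 0.47 points.

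**6. Power.** This used simulated trials with 15 subjects, dispersion 2.4 and a conditional Poisson analysis. Two-sided alpha of 0.20 is an assumption taken from the 80% CI, since protocol 11.7 states none. For one Period 3 deviator, keeping Periods 1-2 gained 82.4 − 81.6 = 0.8 points (3 to 1.5 episodes per day) and 82.2 − 81.3 = 0.9 points (5 to 3). Only these paired differences should be read. With Period 1 alone kept there was no gain, because that analysis uses within-subject contrasts only. The small gain for Period 1 in step 4 is between-subject information recovered by the random effect.

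**7. Three affected subjects, one per sequence (illustration only).** At n = 18 the whole-subject rule gives √(18/15) − 1 = 9.5%, against 3.6-4.2% with one later period lost. At n = 24 it gives √(24/21) − 1 = 6.9%, against 2.7-3.1%. The documents give no rate that supports three.

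**The case against.** - **The table is damaged.** It is split in extraction, and blank cells cannot be charged to the plan. This stands as a condition: the source table should be checked first.
- **Few subjects can benefit.** Protocol 6.7 has subjects domiciled and dosed by staff, so short washouts should be rare, and the same supervision limits prohibited medication. Prohibited medication at entry is exclusion criterion 9 and belongs to the eligibility row, which is not in question. The useful gain is mostly confined to Period 3 intake or a rare short washout. This stands.
- **The larger figures double-count.** If treatment stops after prohibited medication, as protocol 7.2 lists, those subjects are not completers. They already sit in the 37.5% allowance (24 × 0.375 = 9 per part) and may be replaced under protocol 6.3. Taking three more from 18 completers partly counts them twice, and even then 15 remain, the number on which the power statement rests. This stands, and is why the size is given for one subject.
- **Subject-level exclusion is simple and objective.** A period-level rule that left the affected data to judgement would be worse in an open-label study. This stands against a loosely worded rule, but not against one fixed in advance.

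A reader might infer that the exclusions bias the treatment comparison. The documents do not support that: the codes are prespecified, and nothing shows that deviations depend on treatment. A reader might also infer that Table 4-1 contradicts the all-available-data rule. It does not, because that rule operates within the PD set. The two merely sit awkwardly together.

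**Conclusion.** The point holds as a minor, inexpensive improvement. As the table reads, the primary analysis discards treatment periods that a later deviation cannot have touched. Per affected subject in a part, CI widening is 2.3-3.1% under the current rule, against 0.9-1.5% with one later period lost and 1.7-2.8% with Period 1 only. There is no gain when medication was taken before or in Period 1.

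These sizes rest on an assumed correlation of 0.3-0.7, one summary value per period, bases of 24 and 18 per part, and no replacements. Total impact cannot be stated because deviation rates are not given. The study is non-confirmatory, and no stated figure or conclusion of the plan is shown to be wrong.

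**What to change.** Check the source table. If the TRT02 and COMD01 cells are indeed blank, amend the SAP before database lock:

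1. TRT02: exclude only the treatment period that follows the short washout.
2. COMD01: exclude the period of intake and all later periods, by fixed rule and without case-by-case judgement, and keep every treatment period completed before intake. Where intake was before or in Period 1, subject-level exclusion stands.
3. Word the PD set definition so that these two codes act on periods, as TRT01 already does.
4. Add one sensitivity run of the primary model on all treated subjects with diarrhea data.

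Separately, protocol 5.2 says that prohibited medication may require discontinuation, while 7.2 lists it among the circumstances in which stopping is mandatory. These must be reconciled, because they decide whether later periods exist for COMD01 subjects.

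Cost: new wording for two table rows and the set definition, plus one extra model run. The downside is slightly more analysis work and some medication-affected data in the sensitivity run, which should be labelled as such.

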6.1 Primary objective

The primary objectives of this study are to assess the efficacy of:

- Meals with different carbohydrate content on diarrhea
- Supplements such as (psyllium and calcium carbonate) on diarrhea

when LIK066 is administrated immediately before the breakfast.

6.1.1 Variables

The primary endpoint diarrhea will be assessed by the below two variables

1. Daily number of stools with a BSC score of 6 or 7.
2. Daily number of bowel movements

6.1.2 Descriptive analyses

Daily number of stools with a BSC score of 6 or 7 and daily number of bowel movements will be listed by treatment sequence, subject, and visit/sampling time point. Descriptive summary statistics for the observed value and change from baseline will be provided by treatment and visit. Summary statistics will include mean (arithmetic), SD, median, minimum and maximum.

Observed Mean (SD) plot and spaghetti plot of individuals' observed data will be produced by treatment.

6.1.3 Statistical model, assumptions and hypotheses

The primary efficacy hypotheses are that the mean daily number of stools with a BSC score of 6 or 7 /change from baseline in daily number of bowel movements in:

1. the 50% carb group is higher than other groups with lower carbs
2. the no supplement group is higher than other groups with supplement.

The primary analysis will be performed by study part. The daily number of stools with a BSC score of 6 or 7 will be analyzed using a negative binomial mixed effects model with fixed effects of period, treatment, day, the period-by-day interaction, and the treatment-by-day interaction, and a random subject effect. An unstructured covariance matrix will be specified for the repeated observations on a subject within the same period. The least-squares mean and associated 80% CI for the daily number of stools with a BSC score of 6 or 7 for each treatment, and the estimated mean difference between each treatment, the p-value, and corresponding two-sided 80% CI, will be extracted from the model for each day, and summarized. Mean difference will then be exponentiated as ratio between treatments means. Conclusions from the analysis will be based on treatment differences from all 3 days, collectively.

Change from baseline in daily number of bowel movements will be analyzed by a linear mixed effects model with fixed effects of baseline daily number of bowel movements, period, treatment, day, the period-by-day interaction, and the treatment-by-day interaction, and a random subject effect. An unstructured covariance matrix will be specified for the repeated observations on a subject within the same period. Baseline is defined by the last daily measurement before dosing. If day -1 measurement is missing, day -2 or day -3 measurements will be used instead. The least-squares mean and associated 80% CI for each treatment, and the estimated mean difference between each treatment, the p-value, and corresponding two-sided 80% CI, will be extracted from the model and summarized.

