6.1.3.2 Graphical presentation of results

Least-square mean and least-square mean difference between treatments with 80% confidence intervals will be plotted by treatment for daily number of stools with a BSC score of 6 or 7 and daily number of bowel movements.

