6.2.3 Statistical model, assumptions and hypotheses

[figure not shown]
Three-day total number of stools with a BSC score of 6 or 7 per period will be analyzed by a negative binomial mixed effects model with random effect of subject and fixed effects of period and treatment. Change from baseline in three-day total number of bowel movements per period will be analyzed by a linear mixed effects model with random effect of subject and fixed effects of period, treatment and baseline three-day total number of bowel movements. Secondary endpoints including average stool consistency, PH and weight will be analyzed by a linear mixed effects model with random effect of subject and fixed effects of period, treatment, and baseline measurement. The least-squares mean and associated 80% CI for each treatment, and the estimated mean difference between each treatment, the p-value, and corresponding two-sided 80% CI, will be extracted from the model, and summarized.

[figure not shown]

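### Do the per-treatment LS means of BSC 6/7 stools need a stated scale before they can be read as a mean daily number?

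*SAP*

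**What the plan says.** SAP 6.1.3 states a comparative hypothesis. It opens "The primary efficacy hypotheses are that the mean daily number of stools with a BSC score of 6 or 7" and goes on to say that the reference arm (50% carbohydrate, or no supplement) is higher than the others. The model is negative binomial with fixed effects and a random subject effect, and "An unstructured covariance matrix will be specified for the repeated observations on a subject within the same period". The requested output per treatment is "The least-squares mean and associated 80% CI for the daily number of stools with a BSC score of 6 or 7 for each treatment". Only the contrast is given a transformation: "Mean difference will then be exponentiated as ratio between treatments means". On interpretation the section says "Conclusions from the analysis will be based on treatment differences from all 3 days, collectively".

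Three other places bear on the point:

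- SAP 6.1.2 plans observed values by treatment and visit: "Summary statistics will include mean (arithmetic), SD, median, minimum and maximum".
- SAP 6.1.3.2 says "Least-square mean and least-square mean difference between treatments with 80% confidence intervals will be plotted by treatment", without naming an axis scale.
- SAP 6.2.3 says "Three-day total number of stools with a BSC score of 6 or 7 per period will be analyzed by a negative binomial mixed effects model". It asks for LS means and differences, again without a scale.

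Protocol 11.4.2 describes the LS mean in similar terms and mentions no back-transformation. Protocol 11.7 is the only place that states normal subject effects, and it does so for the model used in the power simulation.

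**The concern.** The hypothesis is worded on a mean count, and the model output is described as being for the daily number of stools. On the log scale an LS mean is not a count. Back-transformed at a subject effect of zero, it is the rate of a typical subject and lies below the average over subjects.

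A report could then show two levels for what looks like one quantity: the arithmetic mean of SAP 6.1.2, and a lower model-based value with an 80% CI. Someone wanting the expected stool burden under a given breakfast or supplement might take the lower one, or compare it with the means of 3 and 5 per day in Protocol 11.7. The linear models (bowel movements, consistency, pH, weight) do not have this feature.

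**Working it through.** **The plan's own figures.** Protocol 11.7 needs 5 completers per sequence and assumes 37.5% drop-out: 5 / (1 − 0.375) = 8 per sequence, and 8 × 6 sequences = 48. This reproduces. Power was re-simulated with 1,000 trials per scenario, 5 subjects per sequence, one Poisson count per period and a shared gamma subject effect. The analysis used a log-link Poisson model with a normal subject intercept. The section states no alpha. At two-sided 0.20, assumed here to match the 80% CI, power was 85–90% over both effect sizes and both dispersions, which agrees with the stated 80% or more. At 0.10 it was 77–85% and at 0.05 it was 66–77%. None of this depends on how LS means are displayed.

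**Inputs.** Means are 3 to 1.5 and 5 to 3 per day, with dispersion 2.4 or 1 (Protocol 11.7). The documents do not give the share of over-dispersion that lies between subjects, so a range is shown.

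**Size of the gap.** With a log link and a normal subject effect of variance s², the mean count is exp(LS mean + s²/2). A lognormal subject effect with variance v (mean scaled to 1) has s² = ln(1 + v). So

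exp(LS mean) / mean = exp(−s²/2) = 1/√(1 + v), with v = share × dispersion.

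| Between-subject share | Dispersion 2.4 | Dispersion 1 |
|---|---|---|
| 100% | 1/√3.4 = 0.54 | 1/√2 = 0.71 |
| 50% | 1/√2.2 = 0.67 | 1/√1.5 = 0.82 |
| 25% | 1/√1.6 = 0.79 | 1/√1.25 = 0.89 |
| 0% | 1.00 | 1.00 |

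In the 100% row, a mean of 3 per day would show as 1.63 or 2.12, and 5 per day as 2.71 or 3.54.

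**Check by fitting.** The model was fitted to 12,000 simulated subjects with a true control mean of 3 and all over-dispersion between subjects.

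| Subject effect | Dispersion | exp(LS mean) | Observed mean | Fitted ratio | Observed ratio |
|---|---|---|---|---|---|
| Lognormal | 2.4 | 1.64 | 2.98 | 0.494 | 0.495 |
| Lognormal | 1 | 2.12 | 3.00 | 0.501 | 0.501 |
| Gamma | 2.4 | 1.13 | 2.97 | 0.497 | 0.497 |
| Gamma | 1 | 1.89 | 3.00 | 0.493 | 0.493 |

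The lognormal rows match the closed form. A gamma effect fitted with a normal one gives a larger gap, 1.13/2.97 = 0.38 and 1.89/3.00 = 0.63. That figure moves with the number of observations per subject: with nine per subject, large-sample fits gave 0.25–0.29 and 0.59–0.62.

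**Effect on the contrast.** For treatments 1 and 2, with fixed-effect means m₁ and m₂ on the log scale,

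[exp(m₁) × exp(s²/2)] / [exp(m₂) × exp(s²/2)] = exp(m₁ − m₂).

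The factor cancels if s² is the same under both treatments. It still cancels within each day if the unstructured covariance lets the variance differ by day. With n = 24 and all planned fixed effects, the median fitted ratio stayed at 0.475–0.511 against a true 0.50.

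**What an added population-averaged mean would bring.** With complete data, subject-specific predictions averaged over all subjects equal the arithmetic mean within about 2%. A subject-level bootstrap 80% CI, checked on that arithmetic mean in 4,000 trials of n = 24, covered the truth in 70–77% of trials at dispersion 2.4 and 73–79% at dispersion 1. The shortcut of multiplying by exp(s²/2) works for a lognormal effect. It overshoots by a factor of 1.6–2.0 for a gamma effect at dispersion 2.4 with all over-dispersion between subjects.

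**The case for a change.** The strongest case for a change is that the direction is not in doubt for the kind of model named in Protocol 11.7, that the gap could approach a factor of two or more, and that a descriptive arithmetic mean does not correct a mislabelled model estimate printed beside it. A one-sentence clarification would cost almost nothing. This stands as far as it goes: the scale is missing, and a back-transformed value should not be called a population mean.

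The harm, however, depends on several steps that the SAP does not take:

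- It never says that the per-treatment LS mean is exponentiated. Left on the log scale, it would hardly be mistaken for a stool count.
- It does not state the distribution of the subject effect. A fitted mean-one gamma effect, or a marginal fit, would leave no gap.
- The planned unstructured within-period covariance was not fitted in the checks. Depending on how it is implemented, the ratio could be anywhere from 1.00 down to 0.54 (dispersion 2.4) or 0.71 (dispersion 1), on lognormal assumptions.
- The dispersion of 2.4 comes from a three-times-daily regimen in an earlier study, while this trial doses once daily, so the figures at 2.4 are illustrative.
- SAP 6.2.3 neither exponentiates the three-day totals nor labels their LS means as a daily number.

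SAP sections 1.1 and 2 also place output detail in reporting documents and table shells that are not public. Silence in the SAP therefore does not show that the tables would be mislabelled.

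**Conclusion.** The technical observation is right, but no change to the plan is needed. Model, test, ratios and sample size are sound as written. The hypothesis is comparative, the conclusions rest on treatment differences, no listed objective asks for an absolute level, and the study is declared non-confirmatory. A reader who wants the observed level has the arithmetic means by treatment and visit. These carry no CI, and they describe the level adequately only if drop-out is unrelated to the counts.

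What remains is a gap that an analyst fills when the output is built: giving the scale in the table or axis label, and calling any back-transformed value subject-specific. A population-averaged mean is optional. It would largely repeat the arithmetic mean, and its interval tends to fall short of nominal coverage.

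The size is zero for the planned conclusions. For a back-transformed level it runs from no gap to 0.71 or 0.54 times the mean under a lognormal effect, and lower under a gamma effect. This rests on a log link (implied, not named), a normal subject effect evaluated at zero, and an unknown between-subject share. The statement about ratios also needs the subject effect to have the same distribution under every treatment.
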